COVER PAGE

Study Title: Evaluation of adherence and outcomes in children with functional constipation after implementing a constipation action plan

NCT: *pending*

Date of Document: 18 October 2016

Study Protocol Title

Evaluation of adherence and outcomes in children with functional constipation after implementing a constipation action plan

Principal Investigator, Research Team, and Study Site

Principal investigator: [name] [name] PhD

Co-Investigator: [name], DO

[contact] [contact]

Address: [name]

Study site: Nemours/A.I. DuPont Hospital for Children

Study Title

Evaluation of adherence and outcomes in children with functional constipation after implementing a constipation action plan

Study Population

Children are eligible to participate in the study if they are otherwise healthy children whose primary language is English with no conditions that would predispose them to develop constipation, between the ages of 3 and 8 years of age and meet the ROME IV criteria for functional constipation.

Study Agent and Intervention Description

Implementation of a Constipation action plan tool: a document describing step by step what needs to be done in response to the patient's daily symptomatology of constipation.

Primary Objective

1. To assess compliance in pediatric patients with functional constipation that have been provided a constipation action plan plus educational information.

Outcome measures: compliance

Sticker reward chart review at 3 month visit in addition to constipation/adherence questionnaire at initial visit, 1 month telephone encounter and 3 month follow up visit.

Secondary Objectives

1. To assess improvement of constipation symptoms in pediatric patients with functional constipation that have been provided a constipation action plan and educational information

Outcome measures: symptoms

Assess constipation symptoms by using the constipation/adherence questionnaire involving ROME IV Criteria at enrollment (with demographics), 1 month telephone encounter and 3 month follow up visit.

2. To assess the perceived effectiveness of the constipation action plan from the viewpoint of the family

Outcome measures: perceived effectiveness of the constipation action plan

Assess the perceived effectiveness by an anonymous survey

Study design/methodology

This is a randomized controlled single blind study to measure compliance and outcomes in pediatric patients diagnosed with functional constipation. Participants will be recruited from the Division of Pediatric Gastroenterology and Nutrition at Nemours/A.I. duPont Hospital for Children who are being seen with a complaint of constipation. Children are eligible to participate in the study if they are otherwise healthy children whose primary language is English with no conditions that would predispose them to develop constipation, between the ages of 3 and 8 years old and meet the ROME IV criteria for functional constipation. We will obtain parental permission and assent from children older than 7 years of age from all participants. Each family will receive a randomized packet containing educational information (i.e. definitions, water and fiber intake, toilet sitting and medication information), rewards charts and stickers and half of the families will receive an additional constipation action plan tool. The treatment plan for each participant will be determined based on recommendations from the clinical guidelines for the Evaluation and Treatment of Functional Constipation Infants and Children as published by the North American Society for Pediatric Gastroenterology, Hepatology and Nutrition. The packets containing the additional constipation action plan tool will not be known to the investigator prior to assigning the packet to a family. At the first visit, the families will complete an initial paper questionnaire regarding symptomatology, adherence to the treatment plan and demographics. The questionnaires will not contain any patient identifiers and will be stored securely at Nemours. At 1 month, the co-investigator will call each family and administer a phone survey through REDcap regarding symptomatology and adherence to the treatment plan in the past month. At 3 months, the families will return for a follow up visit with their 3 month reward charts and complete a final paper survey regarding the child's symptomatology and adherence to the treatment plan. The CO-I will upload the questionnaire responses onto REDcap based on the identification number. The families who were randomized into the group that received the constipation action plan tool will be mailed a survey regarding the utility of the constipation action plan and whether or not it was helpful in improving adherence to treatment and outcomes. Once received, the feedback survey will also be uploaded onto REDcap based on the identification number.

Study Schedule

Children will be recruited from November 2016 - October of 2017. Participants will remain in the study for a total of 3 months, or until the '3-month follow up appointment' is completed, but no later than February 2018.

Adverse Event Reporting

All adverse events and serious adverse events in association with this study will be reported immediately to the IRB. An adverse event is defined as any unfavorable medical occurrence in a human subject, including any abnormal sign (abnormal physical exam or laboratory finding), symptom, or disease, temporally associated with the subject's participation in the research, whether or not considered related to the subject's participation in the research. The AE or SAE will be documented in the online secure database and the participant will have the opportunity to withdraw from the study if warranted, further follow up and monitoring will be scheduled as indicated based on the adverse event.

Statistical Analysis Plan

[figure not shown]
Descriptive statistics will be used to determine the distribution of key outcome and predictor variables. Means and standard deviations will be calculated to describe the distributions of continuous variables. Counts and proportions will be calculated to describe the distributions of categorical variables. The effectiveness of the constipation action plan tool will be assessed by comparing the parent/survey-responder's reported adherence of the child to the constipation treatment in the intervention and control groups, at each follow-up survey, using multivariable logistic regression model. The change in effectiveness of the constipation action plan tool will be assessed by comparing the intervention and control groups across waves of the follow-up surveys, using multivariable mix-effects logistic regression model. Differences in demographic characteristics between the groups will be adjusted for during analysis. The association between compliance and constipation outcomes will be examined likewise.

Informed Consent Process

Informed consent will be taken after the patient is seen in the outpatient setting and has agreed to participate in the study. The CO-I will discuss the project details with the family and allow them to return on a subsequent visit to sign the consent and fill out the forms if they feel they require more time to think about participation. The families will be allowed to ask questions regarding the project and all questions will be answered prior to signing the consent form. The families will meet with the CO-I; all information will be provided to the families including a detailed description of the study and an explanation of how this will contribute to the scientific community. Assent will be obtained from all children 7 years of age and above. We will follow the families at 1 month and at 3 months to complete questionnaires and discuss their continued participation in the study. If the families decide they no longer wish to participate in the study they will be withdrawn. Translations will be submitted to the IRB for review and approval before enrolling non-English speaking participants.

Privacy and confidentiality

Each family will be seen in a private room for the visit encounters. In addition, the follow up surveys are completed via private telephone encounters and follow up interviews in private rooms. The CO-I will organize the list of participants and subsequent study identification numbers (as indicated on each packet they will receive) on password protected computer files (excel spreadsheet) on the Nemours server. The excel spreadsheet will be the only document containing PHI. All printed questionnaires are void of PHI and will contain only a participant (ID) number. The CO-I will upload the questionnaires to a secure website (REDCap) using the appropriate participant ID.

For questions or problems, call:

Name: _____

Phone: _____

Constipation Action Plan

To be completed by your child's doctor or nurse so that you know how best to manage your child's constipation

Doing Well: Stools every 1-2 days No straining or pain Stool is soft
	
Daily Medicine Name: Dose: How Often: **Continue stool softeners, high fiber diet, increased fluid intake, exercise and scheduled toilet breaks everyday.
	
Notes:


Constipation worsening: No stool in 2-3 days some pain, or hard stools
	
In addition to your Green Zone medicine, you can:
 
 • Increase your: • If your symptoms do not return to the GREEN zone after 3 days of treatment then add: 	
Notes:

Pay attention: More than 3 stools each day
	
Does child seem to have GI illness (fever, vomiting, watery stools, diarrhea)? Stop constipation medicines for 3 days or until diarrhea resolves -Call doctor for: Refusing liquids, dark urine, loose stools for ___ days
 
No fever, vomiting or signs of illness? Change daily medicine: Dose How often:
	
Notes:

Alert! no stool in 5 or more days Stomach pain, vomiting,
	
 • First, Take: • Second, call your doctor now for help 	
Notes:

Adapted from Stafford B, Wills H, Punati J, Deavenport A, Yin L. Constipation Action Plan. (C) 2012 Children's Hospital Los Angeles. All Rights Reserved

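### The feedback survey for secondary objective 2 is described as anonymous, but the plan files it under an identification number whose key the co-investigator keeps

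*Combined protocol and SAP*

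**What the plan says.** Under Secondary Objectives, the second objective is "To assess the perceived effectiveness of the constipation action plan from the viewpoint of the family". Its only stated measure is: "Assess the perceived effectiveness by an anonymous survey".

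The Study design/methodology section describes the procedure. Families randomized to the tool "will be mailed a survey regarding the utility of the constipation action plan and whether or not it was helpful in improving adherence" and outcomes. The section ends: "Once received, the feedback survey will also be uploaded onto REDcap based on the identification number".

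The Privacy and confidentiality section explains what that number is. "The CO-I will organize the list of participants and subsequent study identification numbers", in a password-protected spreadsheet on the site's server. Of that file it says: "The excel spreadsheet will be the only document containing PHI". Of the forms it says: "All printed questionnaires are void of PHI and will contain only a participant (ID) number". The co-investigator enters the questionnaires in REDCap by participant number.

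**The concern.** A survey is anonymous if nobody on the study team can tell who gave which answer. This one is filed by a number that a study-team member can trace to a family, so it is coded or confidential. The protocol gives the only measure of a stated objective a property that its own procedure removes.

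Two things are at stake. The first is candour. Families are asked whether the study's own tool helped them, and the person who can trace their answers is the one who discussed consent with them and telephoned them at 1 month. Only tool-arm families are surveyed, so there is no control response against which a tendency to answer favourably could be offset. The second is reporting. Readers give some weight to the word *anonymous* when they judge an opinion survey, and here that weight would not be earned.

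**Working it through.** No arithmetic applies. The plan states no figure on this point, and the check is whether the sections agree.

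1. **Stated property.** Secondary Objectives: anonymous. The label is attached to this survey alone; the other questionnaires are described as free of identifiers but are not called anonymous.

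2. **How a returned form is stored.** Study design/methodology: in REDCap, by identification number. To file a form this way, whoever enters it must know which number it belongs to. The word *also* in "Once received, the feedback survey will also be uploaded onto REDcap based on the identification number" puts it on the same footing as the numbered questionnaires described just before it.

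3. **What the form carries.** Privacy and confidentiality: "All printed questionnaires are void of PHI and will contain only a participant (ID) number". Read literally, this covers the mailed survey too. Even if it did not, step 2 would still require the number to be known.

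4. **Who can turn the number into a family.** Privacy and confidentiality: the co-investigator, through the spreadsheet of participants and numbers. "The excel spreadsheet will be the only document containing PHI" confirms that the file is identifiable.

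5. **That person's other roles.** The co-investigator conducts the consent discussion (Informed Consent Process), makes the 1-month call (Study design/methodology) and uploads the questionnaires (Privacy and confidentiality).

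6. **Anything that breaks the link.** No section describes a separate unlinked code for this survey, an independent recipient, or destruction of the list before the surveys come back.

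Steps 2 to 4 form an unbroken chain from response to family, and step 6 finds nothing that cuts it. Step 1 is therefore contradicted by the current text.

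7. **Whether the link is needed.** The Statistical Analysis Plan specifies models for reported adherence and for the association between compliance and constipation outcomes. It specifies no analysis that joins the feedback survey to either. Study arm need not be recovered from the number, because only tool-arm families are mailed the form.

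**The case against.** The strongest reply is that this is loose wording. *Anonymous* appears once, in the objectives list, and may have meant only that the form carries no protected health information. The Privacy and confidentiality section describes coded handling openly. This shows how the word may have arisen, but it does not make a traceable record anonymous, so the contradiction remains.

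Other parts of the reply stand and limit the point:

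- **Size of any bias.** A reader might infer a favourable shift large enough to rival the sampling error of the survey. The documents do not support that. They give no sample size, return rate, response scale or expected proportion finding the tool helpful. The relevant quantity is also only the extra shift caused by traceability. Families would still be answering a survey mailed by the study that treated them, so some courtesy bias could remain on an unnumbered form.
- **What families are told.** A reader might infer that families are misinformed. That cannot be shown: consent pages were removed from the public copy, and neither the survey form nor a cover letter is included. Families who were promised anonymity and believed it might answer freely, although the promise would be untrue. Families told that the survey is coded would not be misled. The effect on candour depends on what they are told and whether they notice a number.
- **Value of the number.** It allows responders to be compared with non-responders, duplicates to be caught and reminders to be targeted. In a one-arm mailed survey, non-response may matter as much as candour, so keeping the number is a defensible choice if it is described correctly.
- **Scope.** Only a descriptive secondary objective is touched.

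**Conclusion.** The inconsistency is real and rests on explicit current text: the survey is labelled anonymous, but as planned it is coded and can be re-identified by the co-investigator. Confidence in that is high. It assumes only that the procedure would be carried out as written.

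The consequence for the data is less certain. Candour on secondary objective 2 may be reduced by an unknown amount; that is a reasonable inference from the co-investigator's several roles, not something the documents show. The consequence for reporting is firmer: repeating the word *anonymous* in the report would claim a protection that was not in place. The randomized comparisons of compliance and symptoms do not use this survey and are unaffected. The matter should be settled before surveys are mailed, because a form returned with a number cannot afterwards be said to have been collected anonymously.

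**What to change.** **Preferred: make the procedure match the label.** Mail the feedback survey without an identification number, and enter each return in REDCap as a stand-alone record marked only as tool arm. Amend the last sentence of the Study design/methodology section to say so, and exempt this form from the Privacy and confidentiality statement that all printed questionnaires carry a number.

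The cost is one unnumbered form and small text changes. The study gives up linkage of opinions to adherence or symptoms, comparison of responders with non-responders, duplicate checks by number and targeted reminders; any reminder would have to go to every tool-arm family. No planned analysis is lost, since the Statistical Analysis Plan contains none that uses the link.

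**Alternative, if the sponsor wants linkage: make the label match the procedure.** Replace *anonymous* with *confidential (coded)* under Secondary Objectives, in the report, and in any family-facing text that uses the word. This costs almost nothing and keeps every use of the number. It corrects the claim but does not reduce any candour bias, and the report should say that responses could be traced by a member of the study team.

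### First-visit adherence has no defined plan, period or rule for untreated children, so it cannot anchor a before-after compliance figure; the planned arm comparisons are not biased by this in expectation

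*Combined protocol and SAP*

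**What the plan says.** In the Combined protocol and SAP, the compliance outcome under Primary Objective consists of a sticker chart review at 3 months "in addition to constipation/adherence questionnaire at initial visit, 1 month telephone encounter and 3 month follow up visit". The initial visit is thus one of three listed questionnaire time points for the primary outcome.

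Study design/methodology describes the first form: "At the first visit, the families will complete an initial paper questionnaire regarding symptomatology, adherence to the treatment plan and demographics". It gives no recall period for this item. The 1-month call does have one: the co-investigator will "administer a phone survey through REDcap regarding symptomatology and adherence to the treatment plan in the past month".

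On the plan itself, the same section says: "The treatment plan for each participant will be determined based on recommendations from the clinical guidelines". It does not say when this is done. Recruitment is of children "who are being seen with a complaint of constipation". The eligibility text neither requires nor excludes earlier treatment. Under Informed Consent Process, the co-investigator may "allow them to return on a subsequent visit to sign the consent and fill out the forms", so some first forms may be completed after the visit at which the child was seen.

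The Statistical Analysis Plan names two models for reported adherence. One is a logistic regression comparing intervention and control at each follow-up survey. The other is a mixed-effects logistic regression comparing them over the follow-up waves. The only adjustment named is for demographic differences between the groups.

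**The concern.** The same description, adherence to the treatment plan, can mean three things at the first visit. For an untreated child there is nothing to report. For a child already on treatment the answer concerns an earlier regimen. For a family that completes the form at a later visit it may concern the plan just started. At 1 and 3 months it means adherence to the plan followed during the study.

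The primary objective is worded as an assessment of compliance in children given the action plan, without mention of a comparison, and its outcome list includes the initial visit. The Statistical Analysis Plan also promises descriptive statistics for key outcomes. A table of compliance at three time points is therefore a likely product, and a reader would take a rise from the first column as improvement. Part of that rise could come only from how untreated children were scored.

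There is also a missed opportunity. Treatment status before entry plausibly predicts later adherence, but the text plans no such variable. The first-visit answer cannot replace it while its low end may combine children who were never treated with children who were treated but not adherent.

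**Working it through.** The text gives no sample size, adherence rate or share of untreated children, so there is no figure of the plan's own to reproduce. All rates and arm sizes below are assumed. The roughly equal allocation is from Study design/methodology ("half of the families will receive an additional constipation action plan tool").

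**1. Within-group rise with no true change.** Let *f* be the share of children untreated at entry and scored non-adherent. Let *a* be true adherence, the same at every time point and in both arms.

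- Initial value = (1 − f) × a
- Follow-up value = a
- Apparent rise = a − (1 − f) × a = f × a

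| a | f = 0 | f = 0.25 | f = 0.50 | f = 0.75 | f = 1.0 |
|---|---|---|---|---|---|
| 0.4 | 0 | 10 | 20 | 30 | 40 |
| 0.6 | 0 | 15 | 30 | 45 | 60 |
| 0.8 | 0 | 20 | 40 | 60 | 80 |

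Entries are percentage points. For a = 0.6 and f = 0.50, the initial value is 0.50 × 0.6 = 0.30, and the rise is 0.60 − 0.30 = 0.30.

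**2. A different assumption.** Let treated children be 50% adherent at entry and later, and untreated children be scored 0 at entry and be 60% adherent at follow-up.

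- f = 0.50: from 0.5 × 0 + 0.5 × 0.5 = 0.25 to 0.5 × 0.6 + 0.5 × 0.5 = 0.55, a rise of 30 points.
- f = 0.25: from 0.75 × 0.5 = 0.375 to 0.25 × 0.6 + 0.75 × 0.5 = 0.525, a rise of 15 points.

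No child for whom change is defined has changed.

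**3. Dependence on scoring.** If untreated children were instead coded not applicable, the treated children in step 2 would show 50% at both times and no rise. Setting that treated-only initial value beside the follow-up value for all children at f = 0.50 would still show 0.55 − 0.50 = 5 points, from the change of denominator alone.

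**4. Between arms.** Under randomization *f* is the same in both arms in expectation. The artefact is f × a in each, and the expected difference is f × a − f × a = 0. In addition, neither planned model names the initial value as a response.

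**5. Chance imbalance in treatment status.** With n per arm, the SD of the between-arm difference in the untreated share is √(2f(1 − f)/n). Multiplying by the 10-point gap in follow-up adherence assumed in step 2 (60% − 50%) gives the SD of its contribution to the arm difference at follow-up.

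| n per arm (assumed), f = 0.5 | SD of imbalance | Contribution to arm difference |
|---|---|---|
| 20 | 0.158 | 1.6 points |
| 30 | 0.129 | 1.3 points |
| 50 | 0.100 | 1.0 point |
| 100 | 0.071 | 0.7 points |

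This is random error, not bias. With a 10-point gap the gain from adjustment is modest; it grows in proportion to the gap.

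**The case against.** The strongest reply is that the plan never analyses a rise from baseline. Both adherence models compare randomized arms on follow-up data. The primary objective speaks of assessing compliance, whereas the first secondary objective speaks of improvement, so the authors named improvement where they wanted it. Listing when a form is given does not define a change-from-baseline endpoint. This stands, and it limits the point to description and to the missing covariate.

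Three further replies also stand. First, the documents do not state that the plan is set at entry or that the sample mixes new and treated children. The timing is an inference, and the mix is only permitted. Second, the questionnaire is not in the supplied text and may already have a recall period or a category for no earlier treatment; a figure in the Statistical Analysis Plan is also not shown. The 15 to 30 points depend on untreated children being scored non-adherent, which is assumed. Third, the plan does not propose first-visit adherence as a covariate, so its weakness in that role is not an error in the plan.

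These replies do not supply a definition of the first-visit item. Nor do they explain why the outcome list has three questionnaire time points while the models use only the follow-up surveys.

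**Conclusion.** The point holds in a limited form. The first-visit adherence item is listed under the primary outcome without a stated plan, period or scoring rule for untreated children. A within-group rise measured from it would be partly an artefact: f × a in general, and 15 to 30 points for f = 0.25 to 0.50 at a = 0.6. It would be zero if every child were already on treatment, which eligibility does not ensure, or if untreated children were left out at both times.

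A reader might infer that the trial's estimate of the action plan's effect is inflated by the same amount. The documents do not support that. The planned comparisons are between randomized arms at follow-up, where a common rise cancels in expectation. What remains for those comparisons is that prior treatment status, a plausible predictor of adherence, is not among the named adjustments. That makes this a cheap improvement and not a threat to the main result.

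**What to change.** - **At entry**, add one question: is the child already on constipation treatment? Ask the adherence item only of treated children, about the regimen in use before the enrolment visit and over a stated period. Fixing the item to that time gives the same meaning to forms completed at a later visit. Collect both answers before the packet is opened, so that they are true baseline values.
- **In the Statistical Analysis Plan**, prespecify treatment status, with prior adherence within the treated group, as a baseline covariate in both logistic models, alongside the demographic adjustment. If the adherence answer is yes/no, this is a three-level factor: untreated; treated and adherent; treated and not adherent.
- **Under Primary Objective**, describe the initial-visit value as a baseline descriptor and state that compliance is judged between arms at 1 and 3 months. This brings the outcome list into line with the models already planned.

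The cost is one added entry question with a skip rule, and a few lines of text. The trial gives up a before-after compliance figure, which could not be interpreted as the item is now described. If the questionnaire already has a category for no earlier treatment and a recall period, the first step reduces to stating them in the protocol.

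### Covariates for the randomised arm comparisons rest on observed demographic differences, and the baseline adherence and symptom answers have no stated role (minor: precision and pre-specification, not bias)

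*Combined protocol and SAP*

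**What the plan says.** The Statistical Analysis Plan compares reported adherence "in the intervention and control groups, at each follow-up survey, using multivariable logistic regression model". It assesses change over time by "comparing the intervention and control groups across waves of the follow-up surveys, using multivariable mix-effects logistic regression model". One sentence deals with covariates: "Differences in demographic characteristics between the groups will be adjusted for during analysis". It lists no variables and gives no criterion for a difference. A further sentence reads: "The association between compliance and constipation outcomes will be examined likewise".

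Baseline data are collected. Under Primary Objective, compliance is measured with the "constipation/adherence questionnaire at initial visit, 1 month telephone encounter and 3 month follow up visit", together with the sticker chart. Secondary Objectives plans the same questionnaire, with Rome IV items, at enrolment and both follow-ups, and the first of these objectives concerns improvement. Under Study design/methodology, at the first visit "the families will complete an initial paper questionnaire regarding symptomatology, adherence to the treatment plan and demographics".

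That section also says: "The treatment plan for each participant will be determined based on recommendations from the clinical guidelines". It does not say whether the initial questionnaire precedes the opening of the packet. The 1-month survey asks about the preceding month, but the first-visit adherence item has no stated reference period. Informed Consent Process lets families come back another day to sign and complete the paperwork.

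**The concern.** In a randomised trial, demographic differences between arms are chance differences. A rule that adjusts for whatever differs makes the model depend on the draw, so the arm-comparison model cannot be written down before the data are seen. Observed imbalance is also a poor guide to which covariates are worth having. What helps precision is how strongly a covariate predicts the outcome, and the natural candidate is the baseline answer to the same question. The trial already pays for that answer, and the arm models do not mention it.

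At stake is a fixed, reproducible model and, if baseline answers are strongly predictive, a modest amount of power.

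**Working it through.** **1. The text side by side.** Both arm models concern follow-up surveys only. The covariate sentence concerns demographics only. Baseline adherence and symptoms appear as measurement time points, and at most fall under the descriptive statistics. They are not named as covariate, stratifier, change-score reference or model wave. Calling the models multivariable does not exclude them, but does not commit to them.

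**2. How often chance would change the model.** The plan has no figure to reproduce. Suppose a difference means p < 0.05 on one of k independent demographics. Under correct randomisation the chance of at least one is 1 − 0.95^k: 14% for k = 3, 23% for 5, 34% for 8, 40% for 10. Both the criterion and k are assumptions.

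**3. Whether that distorts the test.** Simulation: five demographics unrelated to outcome, selected at p < 0.05; 30, 50 or 100 per arm; baseline-to-follow-up odds ratio 1, 3, 6 or 10; 2,000 trials per setting. Null rejection was 4.4% to 7.2% unadjusted and 4.4% to 7.4% with selected demographics, on the same simulated trials. At a treatment odds ratio of 2.5, selection changed power by −0.1 to −1.2 points. So there was no material inflation and no gain.

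**4. What the baseline answer could add.** All inputs are assumed: n per arm from 40 to 100, two-sided 5% Wald tests, conditional log odds ratio 0.9, binary baseline answer with prevalence 50%, adherence rates centred on 50%. With OR_b the baseline-to-follow-up odds ratio, the adherence rate in each arm is

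p = ½[expit(±0.45 − ½ ln OR_b) + expit(±0.45 + ½ ln OR_b)].

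For OR_b = 6, ½ ln 6 = 0.896. The lower rate is ½[expit(−1.346) + expit(0.446)] = ½(0.206 + 0.610) = 0.408, and the upper is 0.592. The unadjusted log odds ratio is 2 ln(0.592/0.408) = 0.744, against 0.9 conditional on baseline.

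Unadjusted power is by exact binomial enumeration. Adjusted power is by simulation, 1,500 runs at each of the 61 sizes, so the error of the average is about √(0.73 × 0.27/91,500) = 0.15 point.

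| OR_b | Rates | Unadjusted power | Adjusted power | Change (points) |
|---|---|---|---|---|
| 1 | 0.389, 0.611 | 0.732 | 0.730 | −0.2 |
| 3 | 0.397, 0.603 | 0.673 | 0.701 | +2.7 |
| 6 | 0.408, 0.592 | 0.578 | 0.649 | +7.1 |

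Changes were taken before rounding. With control-arm adherence at 50% instead, they are −0.2, +2.6 and +6.9.

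**5. Why the average is used.** The unadjusted test is discrete. At a 50% rate its exact size is 5.83% at 74 per arm and 4.44% at 75, and averages 4.98% over 40 to 100. Differences in power at a single n mostly reflect where n falls in that pattern.

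**6. Children with no earlier plan.** If half fall in a separate third category at OR_b = 6, the gain, averaged over ten neighbouring sizes near each of 40, 60, 80 and 100, is +2.7 to +3.8 points. With the same averaging, null rejection is 4.8% to 5.2% unadjusted and 4.9% to 5.2% adjusted.

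The mixed-effects model, and adjustment of adherence for the symptom count alone, were not quantified.

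**The case against.** The sentence may simply mean that the collected demographics will be adjusted for, and multivariable models leave room for baseline terms. A figure under the Statistical Analysis Plan heading is not reproduced in the text available, so absence can be claimed only for the visible text. Every power input is assumed. The questionnaire is not in the documents, so the meaning of the first-visit adherence item, a no-earlier-plan answer and item-level Rome IV responses are all unconfirmed. If forms are completed at a later visit, the answers might not predate the new treatment plan even when the packet is still closed. All of this stands and keeps the point minor. None of it supplies a covariate list or a role for the baseline answers.

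Two stronger readings are tempting. A reader might infer that the rule biases the arm comparison or inflates false positives. Step 3 does not show this for a mechanical imbalance rule. An analyst who reported the smallest p-value over all subsets of five demographics would, in a separate simulation on assumed inputs, reject a true null about 8% to 10% of the time. The plan describes no such search, so this shows only what a named list would rule out. A reader might also infer that demographic adjustment is wrong throughout. It is not: the association between compliance and constipation outcomes is not randomised, demographic adjustment belongs there, and the only gap is the unnamed list.

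**Conclusion.** The point holds as a minor one about pre-specification and precision. The visible plan does not fix the covariates of the randomised comparisons and gives no model role to the baseline answers. Averaged over 40 to 100 per arm, and on the inputs assumed above, adjusting for the baseline answer is worth about 0, +3 or +7 points of power as the baseline-to-follow-up odds ratio goes from 1 to 3 to 6. At an odds ratio of 6 with half the children having no earlier plan, it is worth about +3 to +4. The documents do not show which case applies. The gain for adherence depends on the first-visit item referring to earlier treatment.

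**What to change.** For the randomised arm comparisons, replace the covariate sentence with:

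> Each arm comparison will adjust for the baseline answer to the same outcome, whatever the observed balance: the baseline adherence answer in the adherence models (with a separate category for children with no earlier treatment plan) and the baseline Rome IV symptom count in any symptom comparison. Any demographic covariates will be named before the data are seen and will not be chosen by observed difference. Unadjusted estimates will also be reported.

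A count is needed because every child meets Rome IV at entry, so the yes/no status is constant at baseline. Adjusted and unadjusted odds ratios will differ in size even under perfect balance (0.9 against 0.744 on the log scale in the example), so each should be labelled.

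Keep demographic adjustment, with the same named list, for the compliance–outcome association.

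Add that the initial questionnaire is completed before the packet is opened, and that its adherence and symptom items both refer to the period before enrolment and before the new treatment plan, including when families return later to complete the forms. If the adherence item does not refer to earlier treatment, use only the baseline symptom count and claim no power gain for the adherence models.

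The cost is a few sentences in the analysis plan, one on procedure, and confirmation or addition of the questionnaire items; no new visit is needed. The downside is a few degrees of freedom and essentially no gain (about −0.2 points on average on these inputs) if baseline answers do not predict follow-up.
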